9.4 Accountability

The investigator must keep an accurate account of the number of IMP units delivered to the site, administered to participants, and returned to COMPASS or its designee during and at the completion of the study. The IMP must be administered to participants only by an appropriately qualified person. The IMP is to be used in accordance with the protocol by participants who are under the direct supervision of the investigator. Investigators should maintain records that document adequately that the participants were administered the IMP dose specified by the protocol and reconcile all IMPs received at the site before final disposition. At the end of the study, or as directed, all IMP, including unused, partially used, and empty containers, will be returned to the sponsor or its designee.

9.5 Compliance

Administration of the IMP will be supervised by study personnel to ensure compliance.

10 CONCOMITANT THERAPY

All prescription and non-prescription medications (eg over-the-counter drugs and herbal supplements) that participants report taking during the 30 days prior to screening will be assessed and recorded at that visit. For each medication, documentation should list the trade or generic name, the total daily dose including units (or the dose, units and scheduled and actual frequency of administration if the medication is not taken daily), the route of administration, and the reason for use.

Concomitant medication refers to all drugs and therapies used from the time the ICF was signed through the end of study participation.

Changes, additions, or discontinuations to medications will be assessed and recorded in the eCRF during each study visit. All as-needed (*pro re nata*, PRN) prescriptions should be converted to reflect actual number of pills or dose taken per day.

10.1.1 Permissible Medications

All concurrent non-serotonergic medications are allowed.

Medications for the management of concurrent anxiety and insomnia, or nonpsychiatric medications that have a potential psychotropic effect are permitted within the following limitations. From the initial screening visit through final study visit (EOS), participants are permitted to remain on the same regular dose regimen of benzodiazepines there were already on in order to avoid withdrawal symptoms. Participants who were not taking benzodiazepines before screening may take up to 2 mg of lorazepam equivalents per day for anxiety emerging during the withdrawal of antidepressant and antipsychotic medications if it is not taken within 4 hours before COMP360 administration. Hypnotics such as zopiclone, eszopiclone or zolpidem are allowed for insomnia. Prescription and non-prescription medications with psychoactive properties that are used as needed for nonpsychiatric conditions (eg pseudoephedrine for allergies or cold symptoms;) can be used daily but not within 12 hours before dosing. Documentation of the use of adjunctive anxiolytics, hypnotics or medication with potential psychotropic properties (including over-the-counter preparations) will be obtained at each clinic visit. Amphetamines prescribed for ADHD are permitted.

Therapy considered necessary for the participant's welfare may be given at the discretion of the study clinician.

10.1.2 Definition of Women of Childbearing Potential and/or Acceptable Contraceptive Methods

A woman is considered of childbearing potential (eg fertile) following menarche and until becoming postmenopausal unless permanently sterilised (eg participant had hysterectomy, bilateral salpingectomy, or bilateral oophorectomy).

A woman who is not of childbearing potential is considered to be postmenopausal after at least 12 months without menstruation.

The following methods of contraception, if used properly and used for the duration of the study, are generally considered highly effective:

- Combined oestrogen- and progestogen-containing hormonal contraception associated with inhibition of ovulation:
 - Oral
 - Intravaginal
 - Transdermal
- Progestogen-only hormonal contraception associated with inhibition of ovulation:
 - Oral
 - Injectable
 - Implantable
- Intrauterine device
- Intrauterine hormone-releasing system
- Bilateral tubal occlusion
- Vasectomised partner
- Sexual abstinence

Periodic abstinence (eg calendar, symptothermal, or post-ovulation methods, and tubal ligation/occlusion) is not an acceptable form of contraception for this study.

These methods of contraception also apply to partners of male participants.

The investigator and each participant will determine the appropriate method of contraception for the participant during the participation in the study. This will be documented at screening.

If a participant or the partner of a male participant becomes pregnant during the study, the investigator will notify the PI, study sponsor and COMPASS immediately after the pregnancy is confirmed according to [Section 14.4](#).

10.1.3 Prohibited Medications

Participants are to be discontinued from antidepressant and/or antipsychotic medications at least two weeks prior to baseline visit. These medications include the following two classes of the Anatomical Therapeutic Chemical (ATC) Classification System: - NO5A Antipsychotics & NO6A Antidepressants. Methylphenidate is also excluded. Participants should also discontinue prazosin one week before COMP360 administration session.

The medical monitor should be contacted if there is any question that a used medication is thought to be in one of these classes. These medications are not to be reintroduced to the participant until after week 4. Participants who require concomitant medication(s) specifically for the treatment of PTSD at any time through the duration of the study will be assessed for reasons of resuming their medications and followed until 12 weeks post COMP360 administration. Participants can resume taking prazosin the day after administration session, if necessary. The study clinician should initiate treatment of symptoms of PTSD as deemed appropriate and may change the venue of therapy (eg outpatient to inpatient) if deemed clinically necessary. The intervention may be a combination of somatic (eg approved antidepressant medication) and non-somatic (various forms psychotherapy, eg TF- CBT) whose therapeutic intention is remediation of PTSD symptoms. Because the anticipated half-life of COMP360 is approximately 3 h, and only 1 administration of test product is permitted, no known issues regarding pharmacokinetics or pharmacodynamic interactions are envisioned within approximately 7 days of product administration.

10.1.4 *Rescue Medication*

Rescue medications may be used during and after the administration session.

The decision to medicate a participant will depend on whether the responsible physician judges that they are capable of maintaining the safety of the participant and others without medical intervention.

- Benzodiazepine anxiolytics is the pharmacological intervention of choice in case of acute psychological distress (eg medications such as lorazepam or alprazolam that have a rapid onset, a short time until peak plasma concentration, and a short duration of therapeutic action; the oral route is preferable because IV injection procedures may further exacerbate the participant's anxiety)
- Antipsychotic medications (eg risperidone) should be available in the event that an adverse reaction escalates to unmanageable psychosis.

In case of the development of acute anxiety or psychotic symptoms requiring pharmacological intervention, the participant will be managed appropriately. The participant may be discharged from the clinic when, in the opinion of investigator, the condition has stabilised. The participant will be accompanied home. The site is to be notified by the participant that they have returned home safely, and in the absence of receiving a phone call site staff will directly contact the participant.

Information for how to manage participants during difficult psychological states are detailed in the Therapist Manual.

11 ADVERSE EVENTS

Throughout the course of the study, all AEs will be monitored and recorded in the eCRF, including the AE's description, start and end date, seriousness, severity, action taken, and relationship to the IMP. If AEs occur, the first concern will be the safety of the study participants.

Per ICH E2A: An AE is any untoward medical occurrence in a participant or clinical investigation participant administered a pharmaceutical product and which does not necessarily have to have a causal relationship with this treatment. An AE can therefore be any unfavourable and unintended sign (including an abnormal laboratory finding, for example), symptom, or disease temporally associated with the use of a medicinal product, whether considered related to the medicinal product.

Medical interventions such as surgeries, diagnostic procedures, and therapeutic procedures are not AEs, but the action taken to treat the medical condition. They should be recorded as treatment of the AEs.

The investigator will promptly notify COMPASS or Worldwide Clinical Trials of all SAEs and nonserious AEs occurring during the clinical trial so that legal obligations and ethical responsibilities towards the safety of participants and the safety of the product under clinical investigation are met.

COMPASS or Worldwide Clinical Trials has a legal responsibility to notify both the local regulatory authority and other regulatory agencies about the safety of a product under clinical investigation. COMPASS or Worldwide Clinical Trials will comply with country-specific regulatory requirements relating to safety reporting to the regulatory authority, Institutional Review Board (IRB)/Independent Ethics Committee (IEC), and investigators. These will be detailed in the safety plan.

11.1 Documenting Adverse Events

AEs occurring from when the participant signs the ICF until the last study event will be recorded. Any AEs occurring before the start of treatment (eg before the dose of the IMP on day 1) will be recorded as pre-treatment AEs. Also, the sign, symptom, or disease present before starting the treatment period are only considered AEs if they worsen after starting the treatment period. Investigators should document all significant illnesses that the participant has experienced within 3 months of the screening and up to the day of inclusion. Illnesses first occurring or detected during the study and/or worsening of a concomitant illness during the study are to be documented as AEs.

All clinical laboratory results, vital signs, and ECG results or findings should be appraised by the investigator to determine their clinical significance. Isolated abnormal clinical laboratory test results, vital sign findings, or ECG findings (eg not part of a reported diagnosis) should be reported as AEs if they are symptomatic, lead to IMP discontinuation/study withdrawal, require corrective treatment, or constitute an AE in the investigator's clinical judgment.

At each time point, the investigator will determine whether any AEs have occurred by evaluating the participant. AEs may be directly observed, reported spontaneously by the participant or by questioning the participant at each time point. Participants should be questioned in a general way, without asking about the occurrence of any specific symptoms. The investigator must assess all AEs to determine intensity, causality and seriousness, in accordance with the definitions in Sections 11.2, 11.3, and 12.1, respectively. The investigator's assessment must be clearly documented in the study site's source documentation with the investigator's signature.

Always report the diagnosis as the AE or SAE term. When a diagnosis is unavailable, report the primary sign or symptom as the AE or SAE term with additional details included in the narrative until the diagnosis becomes available. If the signs and symptoms are distinct and do not suggest a common diagnosis, report them as individual entries of AE or SAE.

The investigator should report all AEs on the AE page(s) of the eCRF and source documents, regardless of seriousness, severity, and causality. Whenever possible, an AE will be reported using a diagnostic term, (eg "common cold" or "upper respiratory infection" rather than "runny nose, cough, mild fever") and should be described with the attributes described in Sections 11.2 and 11.3.

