7.2 Study Procedures by Time Point

7.2.1 *Screening Period*

The participant will be seen initially to evaluate suitability for the study. All participants will be seen at the clinic weekly for a minimum of three weeks prior to the baseline visit to ensure safe discontinuation of current antidepressant/antipsychotic medications required by the protocol, and to conduct psychoeducation. At the first screening visit, the following assessments will be performed and recorded:

- ICF
- Medical history
- Prior and current medications; the participant will be tapered from prohibited medications (see [Section 10.1.3](#)), if any, under the supervision of the study clinician
- Review of inclusion/exclusion criteria ([Section 6](#))
- MINI version 7.0.2
- MSI-BPD
- ITQ
- PCL-5
- LEC-5
- CTQ
- CSSRS (Last 12 months)
- Vital signs (ie, supine, after at least five mins of rest, diastolic and systolic blood pressure, pulse, and body temperature)
- Weight

- Height
- 12-lead ECG
- Blood and urine samples for:
 - Clinical laboratory tests
 - Urinalysis
 - Urine drug screen
 - Urine pregnancy test for all women of childbearing potential
- Document contraceptive method to be used by the participant
- If the participant opts to participate in the Measure Health app, the app will be uploaded on the participant's mobile phone and activated

All participants will undergo two in-person preparatory sessions during the screening period, where the designated therapist will use psychoeducational material. More details on the preparatory sessions are in the Therapist Manual.

Once a patient completes all screening assessments and all screening data is entered into the EDC, the Medical Monitor, and CAT Team will review data entered and issue approval, if the patient is eligible. Once approval is issued, the patient should then be invited for a screening V1a visit. The V1a visit is the point at which the patient begins tapering off their antidepressant and/or antipsychotic medications, if appropriate. The patient must complete the taper within the first 4 weeks of this period, prior to 2 weeks completely off antidepressant and/or antipsychotic medications, before baseline. The tapering period used in the study is set at the industry standard for depression trials.

At subsequent screening period visits (V1a, V1b, etc), medications taken and any changes in medications since the previous visit, and the C-SSRS will be obtained.

7.2.2 ***Baseline Visit – Visit 2 – Day -1***

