Clinical laboratory evaluations will be performed including blood chemistry, haematology, urinalysis, urine drug screen, and urine pregnancy test (for women of childbearing potential). Blood samples for clinical laboratory tests will be collected at screening, baseline, and day 2. Urine samples will be collected at screening and baseline. The details of the analyses are listed in Table 8.1. and in the Schedule of Assessments in Section 5.3.

Table 8.1 List of clinical laboratory evaluations

Haematology	Chemistry
Haemoglobin	Albumin
Haematocrit	Alkaline phosphatase
Red blood cell count	Alanine aminotransferase (ALT)
Mean corpuscular haemoglobin	Amylase
Mean corpuscular volume	Aspartate aminotransferase (AST)
Mean corpuscular haemoglobin concentration	Bicarbonate
White blood cell count (with differential)	Bilirubin (direct, indirect, and total)
Platelet count	Calcium
	Chloride
	Creatine kinase
	Creatinine
	Gamma-glutamyl transferase
	Glucose
	Lactate dehydrogenase
	Lipase
	Magnesium
	Phosphate
	Potassium
	Protein-total
	Sodium
	Urea (blood urea nitrogen)
	Uric acid
Urinalysis (dipstick)	Urine Drug screen
Blood	Amphetamines
Glucose	Barbiturates
Ketone	Benzodiazepines
Protein	Cocaine
pH	Cannabinoids
Specific gravity	Opiates
Nitrite	
Leukocytes	
Bilirubin	
Urobilinogen	
Others	
Urine pregnancy dipstick	

8.2.5 *Adverse Events*

All AEs occurring after the participant signs the ICF and up to the last study event will be recorded. Any AEs occurring before the start of treatment (eg, before the dose of the IMP on day 1) will be recorded as pre-treatment AEs. Any SAE ongoing at V12 (EOS/ET) will be followed until resolution or no longer considered clinically significant.

See [Sections 11](#) and [12](#) for additional information.

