10 SAFETY

10.1 Adverse Events (AEs)

An overall summary of AEs, including total number of TEAEs and treatment-emergent serious adverse events (TESAEs), severe TEAEs, AESIs, TEAEs and TESAEs leading to study discontinuation, and TEAEs leading to death will be presented (*Table 14.3.1.1*).

The following summary tables will be summarised by SOC and PT, and sorted by alphabetical order for SOC and by total descending frequency for PT, including both the number of participants with a given event and the number of events.

- Summary of TEAEs (*Table 14.3.1.2*)
- Summary of non-serious TEAEs $\geq 5\%$ (PT for any treatment group $\geq 5\%$) (*Table 14.3.1.3*)
- Summary of TEAEs by worst severity (mild/moderate/severe) (*Table 14.3.1.4*)
- Summary of TEAEs by strongest relationship to COMP360 (related/not related) (*Table 14.3.1.5*)
- Summary of TEAEs by time of onset (see Section 8.3.1 for categories) and duration (see Section 8.3.1 for categories) (*Table 14.3.1.6*)
- Summary of TESAEs (*Table 14.3.1.7*)
- Summary of TESAEs by time of onset (see Section 8.3.1 for categories) and duration (see Section 8.3.1 for categories) (*Table 14.3.1.8*)
- Summary of AESIs (*Table 14.3.1.9*)
- Summary of AESIs by time of onset (see Section 8.3.1 for categories) and duration (see Section 8.3.1 for categories) (*Table 14.3.1.10*)
- Summary of TEAEs leading to study withdrawal (*Table 14.3.1.11*)
- Summary of pre-treatment AEs (*Table 14.3.1.14*)

For each of the summaries done at the participant level, multiple occurrences of the same event within a participant will be counted once in the summaries by SOC and PT; multiple occurrences of the same event within a participant will be counted once in the worst severity category (severe $>$ moderate $>$ mild) and/or strongest study drug relationship category (related $>$ not related). For relationship category, related also includes “possibly related” events. If severity or relationship is found to be missing, the most severe occurrence will be imputed for that particular summary.

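### Protocol 11.1 gives two incompatible rules for symptoms that begin between consent and dosing, so the adverse event record of the medication taper may be incomplete and differ by site

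*Protocol*

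**What the plan says.** Protocol 11.1 opens with the recording window: "AEs occurring from when the participant signs the ICF until the last study event will be recorded". It then classifies what comes before the dose: "Any AEs occurring before the start of treatment (eg before the dose of the IMP on day 1) will be recorded as pre-treatment AEs". The next sentence says that "the sign, symptom, or disease present before starting the treatment period are only considered AEs if they worsen after starting the treatment period". The treatment period is not defined, but the sentence before gives the Day 1 dose as its example of the start of treatment. Two sentences later the same paragraph adds: "Illnesses first occurring or detected during the study and/or worsening of a concomitant illness during the study are to be documented as AEs".

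Protocol 8.2.5 repeats the window ("All AEs occurring after the participant signs the ICF and up to the last study event will be recorded") and the pre-treatment category, but not the worsening sentence.

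On the taper, Protocol 7.2.1 states: "The V1a visit is the point at which the patient begins tapering off their antidepressant and/or antipsychotic medications, if appropriate". That visit comes after consent and screening approval and before the dose. For V1a, V1b and later screening-period visits, the same section says that "medications taken and any changes in medications since the previous visit, and the C-SSRS will be obtained"; it does not name AEs. The schedule in Section 5.3 does tick AEs for the screening period, and Section 7.2.2 lists AEs and SAEs at Baseline.

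SAP 10.1 plans a "Summary of pre-treatment AEs" (Table 14.3.1.14), with a matching Listing 16.2.7.5. In SAP Section 16 both use the Screening Analysis Set, that is, everyone who signed the consent form.

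**The concern.** For a symptom that starts after consent and before the dose, the two consecutive sentences in 11.1 cannot both be followed. The first makes it a pre-treatment AE. The second makes it no AE at all unless it worsens after dosing. Taken literally, the second sentence leaves the category created by the first almost empty.

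The conflict falls on the interval that contains the taper. Stopping antidepressants and antipsychotics is a condition of entry, so symptoms that arise from it belong in the safety record, and AEs are listed among the primary endpoints. Two things are at stake. One is whether the pre-treatment AE table and listing are complete and mean the same at every site. The other is whether, when a condition worsens after dosing, the AE record shows that it began in the taper. The visit list in 7.2.1 does not help a site choose, because it leaves out the AE check that the schedule requires at those visits.

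**Working it through.** The plan gives no figure to reproduce here. The check applies each rule to the same cases and follows the result into the definition of a treatment-emergent AE (TEAE).

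**Inputs**
- Consent rule: Protocol 11.1 (first two sentences) and 8.2.5.
- Worsening sentence: Protocol 11.1 (third sentence).
- TEAE: onset on or after the dose, or a pre-existing condition that worsens on or after it (Protocol 13.5.2.1; SAP 8.3.1).
- A change of intensity category over several days is recorded separately with its own onset date (Protocol 11.2).
- Start-date imputation: SAP 8.3.8.1.

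**Cases: a symptom that begins during the taper**

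| Course | Consent rule | Worsening sentence, read literally |
|---|---|---|
| Resolves before the dose | Pre-treatment AE | Not an AE |
| Persists unchanged through the dose | Pre-treatment AE | Not an AE |
| Worsens after the dose | Pre-treatment AE, plus a TEAE for the worsening | TEAE only, with no earlier AE record |
| Participant is never dosed | Pre-treatment AE | Can never become an AE |

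The rules disagree in every row. The last row matters because Table 14.3.1.14 and Listing 16.2.7.5 include people who consented and were not dosed.

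**Effect on TEAEs.** In the second row the symptom is a TEAE under neither rule. In the third row the worsening is a TEAE under both, as the definition intends; what the literal reading removes is the earlier AE record. An unchanged symptom can become a TEAE only through its date. Under SAP 8.3.8.1, an AE that is ongoing, or that stops on or after the dose, takes the dose date as its start in three situations: the start date is missing; only the year is known and it is the dosing year; or only month and year are known and they match the dosing month. A start date entered wrongly could have the same result.

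**Time at issue.** Taper of up to 4 weeks plus 2 weeks off medication (Protocol 5.1 and 7.2.1) = 6 weeks. Follow-up after dosing = 12 weeks. 6 / (6 + 12) = 6/18 = 33%. This is the maximum for a participant who tapers and uses the full allowance. It measures time under the conflicting rules and says nothing about how many events would be lost.

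**The case against.** The strongest answer is that the intended rule is clear. The later sentence in 11.1 calls illnesses first occurring during the study AEs. Section 8.2.5 repeats recording from consent without the worsening sentence. Section 7 makes the schedule the outline of procedures, and the schedule ticks AEs at screening, through the screening period and at Baseline. Section 7.2.2 lists AEs the day before dosing. Section 5.1 requires frequent contact to watch for withdrawal effects, and 8.2.1 requires significant C-SSRS findings to be reported as AEs or SAEs. The SAP schedule also collects a withdrawal-symptom scale (mDESS) from V1b to Baseline in participants who must stop medication. On this view the worsening sentence is a medical-history rule that was loosely drafted.

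Most of that stands. A reader might infer that symptoms of the taper would leave no trace; the documents do not support this, because the C-SSRS and, under the SAP, the mDESS capture some of them, and a site would have to pass over several instructions to record nothing. A reader might also infer that persisting withdrawal symptoms would be counted against COMP360; that does not follow from either rule without a start date that is wrong, missing or partial.

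The objection does not remove the sentence. An AE check at Baseline is still governed by 11.1, so a site that applies the sentence literally would find the symptom and not class it as an AE. The mDESS is not a substitute: it starts at V1b, it is a self-reported checklist without seriousness or causality, it is absent from the protocol supplied, and it gained a table and a listing only in the post-lock addendum.

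**Conclusion.** The inconsistency is real, and the worsening sentence is wrong as written. Followed literally, it keeps taper-onset symptoms out of the AE record unless they worsen after dosing, so the pre-treatment AE table and listing could be incomplete and could differ by site. The weight of the other text makes recording from consent the likely intent, so this is a drafting fault with a limited effect on a primary safety record.

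No effect size can be given. The number of participants who taper is not stated, and the documents do not show which rule sites followed. One third of study time is tempting to read as the share of events at risk, but it is only an upper bound on time for those who taper.

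The conclusion assumes that the treatment period starts with the Day 1 dose, as the adjacent sentence suggests. It also rests on the protocol supplied. The SAP is based on protocol V5.0 and schedules items (mDESS, BPRS+) that the supplied protocol lacks, so whether 11.1 was reworded in V5.0 cannot be checked.

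**What to change.** In Protocol 11.1, limit the worsening sentence to conditions present before the consent form was signed. Then state the rule for the interval directly, for example: *Any onset or worsening between signature of the ICF and the dose is a pre-treatment AE.* Define the treatment period as starting with the dose. In 7.2.1, add AEs and SAEs to the V1a/V1b procedures so that they match the schedule.

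No separate pre-dose intensity record is needed: 11.1 already requires intensity to be assessed for every AE, and 11.2 already has changes of intensity recorded separately.

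The cost is a few lines of wording. The AE form, schedule tick, table and listing already exist. The downside is somewhat more pre-treatment AE records.

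As the addendum shows that the database is locked, rewording can no longer change what was collected. The clinical study report should state which rule sites applied. Comparing the mDESS listing (16.2.9.7) with Listing 16.2.7.5 would show whether withdrawal symptoms that participants reported before dosing also appear as pre-treatment AEs.
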